7.8.3 Vital signs

The analyses of vital signs (blood pressure, pulse rate), body temperature, and body weight will be descriptive in nature. In primary analysis, descriptive statistics of vital signs and for the difference from baseline (see [Section 6.7](#)) up to week 16 will be provided based on SAF, including the last value, the minimum value and the maximum value up to week 16. In final analysis, descriptive statistics of vital signs and for the difference from baseline (see [Section 6.7](#)) for all visits will be provided based on SAF, including the last value, the minimum value and the maximum value on treatment for Arm 1-4 and, up to and post the first treatment at or after week 16 respectively for Arm 5.

Clinically relevant findings in vital signs data will be reported as baseline conditions (at screening) or as AEs (during the trial) if judged clinically relevant by the investigator, and will be analysed as such.

[figure not shown]
7.8.4 ECG

[figure not shown]
[figure not shown]
Abnormal findings in 12-lead ECG will be reported as baseline conditions (at screening) or as AEs (during the trial) if judged clinically relevant by the investigator, and will be analysed as such.

No separate listing or analysis of ECG data will be prepared.

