5.2 ASSESSMENT OF SAFETY

Safety will be assessed descriptively based on:

- Adverse events (including drug-related AEs and AEs leading to discontinuation)
- Adverse events of special interest (AESIs)
- Serious adverse events (SAEs)
- Intensity of adverse events will be assessed by Rheumatology Common Toxicity Criteria (RCTC) version 2.0 (refer to [Appendix 10.3](#) and ISF for details)
- Safety laboratory tests
- Physical examination
- Vital signs (blood pressure, pulse rate, body temperature, respiratory rate)
- 12-lead Electrocardiogram (ECG)
- Local tolerability
- Immunogenicity (ADA/Nab)

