5.2.4 Electrocardiogram

The 12-lead ECGs must be administered by a qualified technologist and results will be recorded as scheduled in the Flow Chart. The investigator or a designee will evaluate whether the ECG is normal or abnormal and assess clinical relevance. ECGs may be repeated for quality reasons and a repeated recording used for analysis. Additional ECGs may be recorded for safety reasons. Dated and signed printouts of ECG with findings should be documented in patient's medical record.

Clinically relevant abnormal findings will be reported either as baseline condition (if identified at the screening visit) or otherwise as AEs and will be followed up and/or treated as medically appropriate.

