7.2.5 Safety analyses

Adverse events will be coded using the current version of Medical Dictionary for Regulatory Activities (MedDRA) coding dictionary. Standard BI summary tables and listings will be produced.

[figure not shown]
All randomised and treated patients will be included in the safety analysis. In general, safety analyses will be descriptive in nature and will be based on BI standards. No hypothesis testing is planned. Statistical analysis and reporting of adverse events will concentrate on treatment-emergent adverse events (TEAE). To this end, all adverse events occurring between start of treatment and end of the residual effect period will be considered 'treatment-emergent'; the residual effect period (REP) is defined as 16 weeks after the last dose of trial medication. Adverse events that start before first drug intake and deteriorate under treatment will also be considered as 'treatment-emergent'.

Frequency, severity, and causal relationship of adverse events will be tabulated by system organ class (SOC) and preferred term after coding according to the current version of the MedDRA at database lock.

Laboratory data will be analysed both quantitatively as well as qualitatively. The latter will be done via comparison of laboratory data to their reference ranges. Values outside the reference range as well as values defined as clinically relevant will be highlighted in the listings. Treatment groups will be compared descriptively with regard to distribution parameters as well as with regard to frequency and percentage of patients with abnormal values or clinically relevant abnormal values.

Vital signs, physical examinations, or other safety-relevant data observed at screening, baseline, during the course of the trial and at the end-of-trial evaluation will be assessed with regard to possible changes compared to findings before start of treatment.

Immunogenicity data will be analysed in a descriptive way.

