4. CHANGES IN THE PLANNED ANALYSIS OF THE STUDY

All analyses stated in the CTP (latest version) will be performed as planned with the following adaptations.

In the CTP, MMRM model for % change in PPP ASI from baseline will include baseline visits, visits 6, 7, 8 and 9. In TSAP, the visits 3, 4 and 5 are also included.

In the CTP, for the continuous secondary endpoint of percent change in PPP ASI from baseline at Week 52, the following maintenance treatment comparisons will be performed using an MMRM (incorporating weeks 4, 12, 20, 28, 36, 44, and 52). In TSAP, the visits including week 28, 40 and 52 will be included in addition to the visits included for primary analysis at week 16.

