Tuberculosis infections	BICMQ Narrow sub-search 8.2 “Tuberculosis related terms”
Malignant tumours	Narrow Sub-SMQ “Malignant tumours” Narrow Sub-SMQ “Haematological malignant tumours” Narrow Sub-SMQ “Non-Haematological malignant tumours”
Malignant skin tumours	Broad Sub-SMQ “Skin malignant tumours”
Skin melanomas	HLT Skin melanomas (excl. Ocular)
Non-melanoma skin cancer (NMSC)	Broad sub-BICMQ “Skin Malignancies excluding melanomas”
Malignancies excluding NMSC	Sub-SMQ “Malignant tumours” excluding broad sub-BICMQ “Skin Malignancies excluding melanomas”
3-point MACE	BICMQ 3-MACE with subsearch 1.1 narrow and subsearch 1.2 narrow *
Torsades de pointes	Broad SMQ “Torsades de pointes/QT prolongation”
Severe infections (according to RCTC grading)	SOC Infections and infestations of at least severe RCTC grade, by HLGT

* this is achieved by retrieving all cases found either by running subsearch 1 in narrow scope (BICMQ search ID 32019093) or subsearch 2 (BICMQ search ID 32019094)

The frequency of patients with AEs will be summarised by treatment, primary system organ class and preferred term. AEs which were considered by the investigator to be drug related will be summarised separately. Separate tables will also be provided for patients with SAEs, patients with AESIs, patients with AE leading to discontinuation of the trial medication, and patients with other significant AEs (as described previously). AEs will also be summarized by maximum intensity.

For disclosure of AE data on ClinicalTrials.gov, the frequency of patients with non-serious AEs occurring with an incidence of greater than 5 % (in preferred terms) will be summarised by treatment, primary system organ class and preferred term. The frequency of patients with SAEs and drug related SAEs will also be summarised respectively.

For disclosure of AE data in the EudraCT register, the frequency of non-serious AEs with an incidence of greater than 5 % (in preferred terms) and the frequency of SAEs will be summarised.

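### The SAP drops the separate descriptive ECG assessment that Protocol 5.2 foresees, without declaring it, so ECG abnormalities not judged clinically relevant are not compared between arms

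*SAP*

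**What the plan says.** **Protocol.** Section 5.2 opens with "Safety will be assessed descriptively based on" and then gives a list. The 12-lead ECG is one item in it, separate from adverse events, laboratory tests and vital signs. Section 5.2.4 asks the investigator or a designee to rate each ECG as normal or abnormal and to assess its relevance, and adds: "ECGs may be repeated for quality reasons and a repeated recording used for analysis". Clinically relevant abnormalities become baseline conditions or adverse events. Section 7.2.5 provides for a comparison with the state before treatment. It names two kinds of data, the physical examination and the vital signs, and closes with a general class: "other safety-relevant data observed at screening, baseline, during the course of the trial and at the end-of-trial evaluation will be assessed". The ECG is not named.

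**SAP.** Section 7.8.4 consists of two statements. The first is the reporting route: "Abnormal findings in 12-lead ECG will be reported as baseline conditions (at screening) or as AEs (during the trial) if judged clinically relevant". The judgement is left to the investigator, and the findings are then analysed in that form. The second is: "No separate listing or analysis of ECG data will be prepared". Section 4 says: "All analyses stated in the CTP (latest version) will be performed as planned with the following adaptations". It lists two adaptations, both about which visits enter an MMRM. The only other ECG-related output is the search "Torsades de pointes/QT prolongation" in Table 7.8.1: 1, which runs on coded adverse events.

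**The concern.** If the protocol meant ECG results to appear only through adverse events, its separate ECG item in 5.2 would add nothing, and there would be no need to say which recording counts when one is repeated. The SAP leaves only the adverse event route. That route depends on one investigator's judgement about one patient at a time.

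A descriptive table by arm serves a different purpose. It can show that a change from normal to abnormal, unremarkable in each single patient, is more frequent on active drug or at higher doses. Under the SAP such a pattern would appear in no comparison of arms. The trial is meant to define a dose range for Phase III on safety as well as efficacy, and it records ECGs in PPP patients during a year of treatment. The ECG findings that Protocol 1.2 reports come from healthy volunteers after single doses or four weekly doses.

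**Working it through.** The plan gives no figure to reproduce. The check compares sections and then counts recordings.

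**1. How the SAP treats ECG beside similar measures**

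| Measure | Own item in Protocol 5.2 | Clinically relevant findings go to baseline conditions or AEs | Separate descriptive summary in the SAP |
|---|---|---|---|
| Laboratory | yes | yes (SAP 7.8.2) | yes: values, differences from baseline, shift tables |
| Vital signs | yes | yes (SAP 7.8.3) | yes: values, differences from baseline |
| ECG | yes | yes (SAP 7.8.4) | none |

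The SAP uses the same adverse event route for all three measures. Only for the ECG does that route replace the descriptive summary. So the route was not regarded as sufficient for laboratory data or vital signs.

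**2. What reaches a comparison of arms**

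- Abnormal, clinically relevant: tabulated by arm as an adverse event, and open to the Torsades/QT search.
- Abnormal, not clinically relevant: no table by arm and no separate listing. The search cannot retrieve it, because it was never coded as an adverse event.

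**3. Number of recordings**

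Inputs: 140 patients split 40/20/20/20/40, with 40 on placebo (Protocol 3.1); seven marks in the ECG row of the Flow Chart. The marks stand at screening, Day 1, Week 4, Week 16, Week 28, Week 40 and one late visit, whose column is uncertain in the extracted table.

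- All scheduled recordings: 140 × 7 = 980.
- After baseline: 140 × 5 = 700.

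Most of the 700 cannot support a comparison with placebo. Arm 5 receives placebo only before Week 16 (SAP 6.1 and 6.3). At the Week 16 visit the recommended order puts the ECG before dosing (Protocol 6.2), so that recording still belongs to the placebo period. Two post-baseline ECGs per patient remain:

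- Placebo-controlled recordings: 140 × 2 = 280.
- On placebo: 40 × 2 = 80.
- On active drug: 100 × 2 = 200.

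These are upper limits that assume no dropout and no missed ECG. In an arm of 20, one patient is 1/20 = 5 percentage points, so a table would show only large imbalances.

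**The case against.** The case for leaving the SAP as it is has several parts.

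- **The protocol promises no ECG table.** Section 5.2 names the ECG as a basis for descriptive assessment without specifying an output, and the sentence on repeated recordings only says which recording counts. A reader might infer that Protocol 7.2.5 expressly requires ECG change from baseline. It does not: the ECG is covered there only through the general term for other safety-relevant data. This stands, and it limits the force of the contradiction.
- **ECG safety is not left unanalysed.** A reader might take SAP 7.8.4 to cancel all ECG analysis. The statement excludes a separate analysis. Relevant findings are tabulated as adverse events, as Protocol 5.2.4 foresees. This also stands, and it confines the gap to the other abnormalities.
- **The charge of an undeclared change may rest on a superseded protocol.** SAP Section 4 refers to the latest protocol version. The SAP is dated July 2020 and mentions an open-label extension (1368.24) that the supplied Version 1.0 of April 2019 does not mention. A later version may have changed the ECG text. This cannot be settled from the documents.
- **No ECG risk is identified.** Protocol 1.2 reports no clinically relevant ECG changes in the single-dose and multiple-dose volunteer studies, and the table of hypothetical risks in 1.4.2 has no cardiac entry. An independent DMC reviews all available unblinded safety data (SAP 7.10). This lowers the priority. It does not explain why the ECG is treated differently from vital signs.
- **The rating may not be in the database.** Protocol 5.2.4 asks for signed printouts in the medical record and names no CRF field. This stands, and the fix has to depend on it.

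SAP Section 7 also says in general that individual values of all patients will be listed, which sits badly with 7.8.4. The specific ECG statement should govern, and a listing would not compare the arms in any case.

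**Conclusion.** The point holds in a limited form. Measured against protocol Version 1.0, the SAP removes a separate descriptive ECG assessment that Protocol 5.2 foresees, and Section 4 does not say so. What is lost is the comparison between arms of ECG abnormalities not judged clinically relevant. Its placebo-controlled part is at most 280 recordings, 80 of them on placebo.

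A reader might go further and conclude that 980 recordings are wasted, or that a cardiac signal is likely to be missed. The documents support neither. The larger count includes the two baseline-period recordings and the visits after Arm 5 has switched to active drug, and nothing in the documents points to an ECG effect. The primary endpoint, the MCPMod analysis and the reporting of clinically relevant ECG events are unaffected.

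The conclusion assumes that no later protocol version changed the ECG text and that the sponsor's reporting standards, which were not supplied, add no ECG output. It is a cheap improvement of modest weight.

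**What to change.** **If the investigator's rating is in the database,** replace the last sentence of SAP 7.8.4 with text such as:

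> The investigator's ECG rating (normal; abnormal, not clinically relevant; abnormal, clinically relevant) will be tabulated by treatment arm as a shift from the last ECG before the first dose to each scheduled visit and to the worst post-baseline rating. The table will cover the period up to Week 16 on the SAF and, without a placebo comparison, the period after Week 16 on the SAF-post 16. Abnormal ECGs will be listed.

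The text should add that a recording repeated for quality replaces the one it repeats. Otherwise the rule in SAP 6.7 for two observations on the same day would select the worse one.

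**If the rating is not in the database,** declare in SAP Section 4 that the separate descriptive ECG assessment of Protocol 5.2 will not be done, and give the reason.

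**Cost.** The first option needs one more table and one listing, with no new trial procedure. Its downside is that local, unadjudicated ratings in small arms need cautious interpretation. The second option costs one or two sentences.

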7.8.5 Local tolerability

Local tolerability will be summarized by visit, with the frequency and percentage of patients who experienced any symptoms by severity/intensity.

7.9 ANALYSIS OF COVID19 IMPACT

There is currently an outbreak of respiratory disease, COVID-19 worldwide which has impacted the conduct of this trial. This public health emergency has raised more difficulties for patients to meet protocol-specified procedures, including administering or using the investigational product or adhering to protocol-mandated visits and laboratory/diagnostic testing. Site personnel or trial subjects are also under the risk to get infection with COVID-19.

Consequently, there are unavoidable protocol deviations due to COVID-19 illness and/or COVID-19 public and individual health control measures. To assess the impact on patients' safety and drug efficacy in this trial, the following analyses are planned:

Disposition and iPD:

Frequency of the patient with missed relevant visits or early discontinued from study treatment due to COVID-19 and related iPDs will be listed.

Efficacy endpoints:

To evaluate the impact of COVID-19 on efficacy analysis, the following estimand is implemented.

- Alternative estimand (EC-E19) whereby any data collected after use of any rescue therapy or after the first visit with missing treatment due to COVID-19 or after 6 weeks following last treatment before or at discontinuation (to allow for incorporation of the continuing maximum treatment effect period) are censored.

For the percent change in PPP ASI, a similar MMRM model to that used in the primary analysis will be performed.

For PPP ASI50, PPP ASI75 and PPP PGA clear/almost, descriptive statistics will be displayed.

AE based on the periods of COVID-19 disruption

To assess whether there was any potential change in AE assessment during the COVID-19 disruption, AEs prior the disruption, during the disruption and post the disruption (for final analysis only) will be reported separately. It will include the following AE tables,

- Overview on TEAE
- TEAE by SOC, preferred term
- Serious TEAE

The start date for the COVID-19 disruption is chosen to be 1st March 2020 and the end date will be updated in future revision for final analysis.

In addition, if there is any case, AE related to COVID-19 infection will be reported separately.

7.10 HANDLING OF DMC ANALYSES

[figure not shown]
A fully external DMC, independent of the trial and project teams, will be set-up to review all available un-blinded safety data as well as selected efficacy data at regular intervals following first-patient-in. A separate DMC SAP which describes the analyses required for assessment by the DMC will be produced. Further details are provided in a DMC charter.

9. ADDITIONAL SECTIONS

9.1.1 PPP ASI and related endpoints

The Palmoplantar Pustulosis Psoriasis Area and Severity Index (PPP ASI) is an investigator assessment of the extent and severity of pustular and plaque lesions on the palms and soles presenting in PPP patients. The adaptation from PASI, an established measure of severity and area of psoriatic lesions in patients with psoriasis, will be used in this trial ([Table 9.1.1: 1](#)).

This tool provides a numeric scoring for patients overall PPP disease state, ranging from 0 to 72. It is a linear combination of the percent of surface area of skin that is affected on the palms and soles of the body and the severity of erythema, pustules, and scaling (desquamation).

Table 9.1.1: 1 Palmoplantar Pustulosis Psoriasis Area and Severity Index

Score	0	1	2	3	4	5	6
Erythema (E)	None	Slight	Moderate	Severe	Very severe		
Pustules (P) (total)	None	Slight	Moderate	Severe	Very severe		
Desquamation (D) (scaling)	None	Slight	Moderate	Severe	Very severe		
Area affected (in%)* (A)	0	<10	10<30	30<50	50<70	70<90	90 - 100

* where area assessed is glabrous skin on the palms/ soles

The Palmoplantar Pustulosis Psoriasis Area and Severity Index (PPP ASI)

The PPP ASI is calculated as follows as a weighted sum of the scores obtained for E, P, D and A in [Table 9.1.1: 1](#):

$$\begin{aligned}
 \text{PPP ASI} = & [(E+P+D) \times A \times 0.2 \text{ (right palm)}] \\
 & + [(E+P+D) \times A \times 0.2 \text{ (left palm)}] \\
 & + [(E+P+D) \times A \times 0.3 \text{ (right sole)}] \\
 & + [(E+P+D) \times A \times 0.3 \text{ (left sole)}]
 \end{aligned}$$

Missing values for severity or area of involvement will not be imputed. If at least one of these values is missing, then the PPP ASI score will also be considered to be missing. However, individual items and subscores may be presented as applicable.

Achievement of Decrease in PPP ASI \geq xx% (PPP ASI_{xx})

Achieving a response of xx% or larger decrease from baseline in PPP ASI score is denoted as PPP ASI_{xx}. The PPP ASI_{xx} represents a binary variable with values of 0 (= non-response) or 1 (=response).

It is calculated based on the following approach (with xx typically taking a value of 50, 75 or 90):

$$\text{If } \left\{ \frac{PPP ASI (BL) - PPP ASI (current)}{PPP ASI (BL)} \times 100 \right\} \geq xx$$

then PPP ASI_{xx} = 1,

else PPP ASI_{xx} = 0.

PPP ASI severity (by component)

Within each component (E, P or D), the mean severity across all body areas (both palms and both soles) is calculated and presented for each component separately. For example, for Erythema, present $(E_{\text{right palm}} + E_{\text{left palm}} + E_{\text{right sole}} + E_{\text{left sole}})/4$.

Within a component, a missing value in one body area leads to a missing value for the component.

Present the results separately “(by component)”.

PPP ASI severity (by palms or soles)

Among the two palms only, calculate the PPP ASI (palms) score via the components E, P, or D as well as the area (A) but replacing the region factor of 0.2 with a factor of 0.5 (total range combining both palms of 0 to 72):

$$PPP ASI (palms) = 0.5 * \{ [(E_{\text{right palm}} + P_{\text{right palm}} + D_{\text{right palm}}) \times A_{\text{right palm}}] + [(E_{\text{left palm}} + P_{\text{left palm}} + D_{\text{left palm}}) \times A_{\text{left palm}}] \}$$

If at least one of the two palms has a missing value, then the PPP ASI (palms) score will be missing.

Repeat for the PPP ASI (soles) score but replacing the region factor of 0.3 with a factor of 0.5.

Present results separately for each of “(palms or soles)”.

Palmoplantar Pustulosis Severity Index (PPP SI)

PPP SI will be based on severity scores of individual components of PPP ASI assessments. The most severely affected area based on pustules is identified by the investigator at baseline and the same area is assessed in all subsequent visits.

Table 9.1.1: 2 Palmoplantar Pustulosis Severity Index (PPP SI)

Score	0	1	2	3	4
Erythema (E)	None	Slight	Moderate	Severe	Very severe
Pustules (P) (total)	None	Slight	Moderate	Severe	Very severe
Desquamation (D) (scaling)	None	Slight	Moderate	Severe	Very severe

PPP SI total score = E+P+D

Missing values for any subscore will not be imputed. If at least one of these values is missing, then the PPP SI score will also be considered to be missing. However, individual subscores may be presented as applicable.

The sum score for the worst area represents the PPP SI (range 0-12).

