3.3.2 Inclusion criteria

1. 18 to 75 years of legal age (according to local legislation) at screening.
2. Diagnosis of Palmoplantar Pustulosis defined as presence of primary, persistent (>3 months duration), sterile, macroscopically visible pustules on the palms and/or soles, without or with plaque psoriasis elsewhere on the body.
3. Presence of white or yellow pustules on palms and/or soles at screening and baseline.
4. Pustular severity score ≥ 2 in at least one region and ≥ 10 well-demarcated pustules (white or yellow pustules) across all regions at screening and baseline.
5. PPP PGA of at least moderate severity (≥ 3) at screening and baseline.
6. A minimum PPP ASI score of 12 at screening and baseline.
7. Male or female patients. Women of childbearing potential (WOCBP)¹ must be ready and able to use highly effective methods of birth control per ICH M3 (R2) that result in a low

¹ A woman is considered of childbearing potential (WOCBP), i.e. fertile, following menarche and until becoming post-menopausal unless permanently sterile.

Permanent sterilisation methods include hysterectomy, bilateral salpingectomy and bilateral oophorectomy. Tubal ligation is NOT a method of permanent sterilisation.

failure rate of less than 1% per year when used consistently and correctly. A list of contraception methods meeting these criteria is provided in the patient information and in [Section 4.2.2.3](#).

8. Signed and dated written informed consent in accordance with ICH-GCP and local legislation prior to admission to the trial.

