10. APPENDICES

10.1 INSTRUCTIONS FOR USE

10.1.1 Palmoplantar Pustulosis Area and Severity Index (PPP ASI)

Score	0	1	2	3	4	5	6
Erythema (E)	None	Slight	Moderate	Severe	Very severe		
Pustules (P) (total)	None	Slight	Moderate	Severe	Very severe		
Desquamation (D) (scaling)	None	Slight	Moderate	Severe	Very severe		
Area affected (%)*	0	<10	10<30	30<50	50<70	70<90	90 - 100

* where area assessed is glabrous skin on the palms/ soles

PPP ASI = [(E+P+D) Area x 0.2 (right palm)] + [(E+P+D) Area x 0.2 (left palm)] + [(E+P+D) Area x 0.3 (right sole)] + [(E+P+D) Area x 0.3 (left sole)]

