6.6.2 Efficacy data

Based on the different reasons for patients' data missing for different endpoints, various approaches will be used to assess the impact of missing data on the efficacy endpoints of this trial, depending upon the type of the endpoint (cf. [Table 6.3: 1](#)). Approaches to be applied are described below.

Missing data imputations of PPP Pain VAS, PPP PGA and PPP ASI related endpoints at the primary analysis of the trial may be performed using all data up to the first maintenance dose at or after week 16 if available. Missing data imputations of other endpoints at the primary analysis will be performed using all data up week 16.

Continuous efficacy endpoints

For efficacy endpoints which are continuous in nature, the use of a restricted maximum likelihood (REML)-based mixed model repeated measures (MMRM) approach as the primary method, if applicable, will ensure that missing data are handled implicitly, via a missing at random (MAR) assumption, by the statistical model.

In order to check the robustness of MMRM method to missing data, a sensitivity analysis will be performed using Multiple imputation with jump to reference method (only for primary analysis at week 16):

As the first step, the non-monotone missing data of PPP ASI total score will be imputed using Markov Chain Monte Carlo (MCMC) simulation and standard techniques. 100 imputations will be performed to ensure adequate efficiency and stability of the estimation for missing data. In a second step, for each imputation, the monotone missing data of patients that were still ongoing in the trial will be imputed once by standard sequential linear regression MI including treatment as categorical covariate and PPP ASI from baseline up to week 16 as

continuous covariates (other missing values will also be imputed as a by-product but subsequently deleted).

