For all binary endpoints (i.e. endpoints that are either 1 (patient responded) or 0 (patient did not respond)), the following will be performed as the primary imputation approach (analysis type: No Response Imputation [NRI]):

- If there are data at visits both before and after the visit with a missing outcome, then impute as success only if both neighbouring visits also represent a success (independent of whether the preceding and following observations were selected for analysis based on time windows described in [Section 6.7](#) and no rescue treatment has been given during this period);
- Otherwise, impute as a failure to achieve a response

Other imputation scheme will be also considered for analysis of the secondary binary efficacy endpoints.

- Best response imputation (BRI): impute all missing values based on the best response observed for the patient at visits prior to withdrawal/occurrence of missing data (independent of whether the observations were selected for analysis based on time windows described in [Section 6.7](#)). If there is no non-missing data available (including baseline), then the missing value will be imputed as a failure.

OC and OC-IR methods will be also used to display the binary data.

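### SAP 9.1.1 discards PPP ASI scores that the recorded items still determine exactly, when a region with zero area or zero severity has another item blank (minor)

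*SAP*

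**What the plan says.** SAP 9.1.1 and Protocol 10.1.1 define the score in the same way. Each palm has weight 0.2 and each sole 0.3, and each weight multiplies the severity sum (E+P+D) and the area grade A of that region. SAP 9.1.1 adds: "This tool provides a numeric scoring for patients overall PPP disease state, ranging from 0 to 72".

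On blanks, SAP 9.1.1 says "Missing values for severity or area of involvement will not be imputed", and then: "If at least one of these values is missing, then the PPP ASI score will also be considered to be missing". It makes no exception for a region with no affected area or no severity. The palms and soles scores are likewise missing if either side has a missing value.

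A missing score then takes one of two routes under SAP 6.6.2. The continuous primary endpoint goes to the MMRM under missing at random. PPP ASI50 and ASI75 go to non-response imputation. There, if data exist on both sides of the gap and no rescue was given, "then impute as success only if both neighbouring visits also represent a success"; the default is "Otherwise, impute as a failure to achieve a response". For these endpoints, imputation at the Week 16 analysis "may be performed using all data up to the first maintenance dose at or after week 16 if available".

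Protocol 3.3.2 admits patients with "macroscopically visible pustules on the palms and/or soles", so a patient can enter with wholly unaffected regions.

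**The concern.** Because area multiplies severity, a region can contribute exactly 0 whatever its blank item would have been. Keeping the score in that case is arithmetic, so it does not conflict with the decision not to impute items. The rule as written nevertheless removes the whole score, including the three regions that were fully recorded.

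Unaffected regions can exist at entry, and treatment is meant to create more of them. If blanks were more frequent in cleared regions, the loss would depend on the patient's state at that visit, which is not what the MMRM's missing-at-random assumption describes. For ASI50 and ASI75 a determined responder would be counted as a failure. At stake are a few values of the primary endpoint and of two binary secondary endpoints.

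**Working it through.** **Inputs.** Formula, weights, score range and missing rule: SAP 9.1.1. Imputation rules: SAP 6.6.2. Visit windows and dosing cut-off: SAP 6.1 and 6.7. Planning model (SD 35, values below -100 set to -100, means after truncation of -25 for placebo and -55 for the high dose): Protocol 7.5. The share q of ASI75 responders with such a blank at Week 16 is an assumption; no document gives it.

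**1. Reproduce the stated range.** Maximum = (4+4+4) x 6 x (0.2+0.2+0.3+0.3) = 72; minimum = 0. This agrees with the SAP. Items: 4 regions x 4 = 16.

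**2. When is a score with one blank still determined?** All 5 x 5 x 5 x 7 combinations for a region were enumerated, blanking one item at a time.
- E, P or D blank: the contribution is known if and only if A = 0.
- A blank: the contribution is known if and only if E = P = D = 0.
- One zero severity is not enough. With E = 0, P = 1, D = 1 and A blank, the unweighted contribution can be 0, 2, 4, 6, 8, 10 or 12.

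**3. One patient.** Baseline 20. At Week 16 both palms have A = 0 with severities blank, and each sole has E+P+D = 4 and A = 2. Score = 0.3 x 4 x 2 + 0.3 x 4 x 2 = 4.8. Reduction = (20 - 4.8)/20 = 76%, an ASI75 response. Under SAP 9.1.1 the score is missing.

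**4. Can bracketing restore the response?** At the Week 16 analysis, data stop at the Week 16 dose for a patient dosed on time, and the efficacy assessment precedes that dose. There is normally no following value, so the result is a failure. The exceptions are a further complete pre-dose assessment in the Week 16 window (Days 100 to 127) and a patient who missed the Week 16 visit. At the final analysis a Week 20 value could bracket the gap. One such patient is worth 1/20 = 5 points in an arm of 20, or 1/40 = 2.5 points in an arm of 40.

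**5. Size across an arm.** Let m be the arm mean, p the share with at least 75% improvement and r the mean among them. If a share q of these scores is lost, the observed-case mean is (m - q p r)/(1 - q p). The planning model gives p = 7.7% and p r = -6.82 for placebo, and p = 30.2% and p r = -27.53 for the high dose. At q = 5%:
- high dose: (-55 + 0.05 x 27.53)/(1 - 0.05 x 0.302) = -54.45
- placebo: (-25 + 0.05 x 6.82)/(1 - 0.05 x 0.077) = -24.75

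The difference is 29.7. ASI75 rates are multiplied by (1 - q) if nothing is bracketed:

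| q | Observed-case mean difference | ASI75, high dose vs placebo |
|---|---|---|
| 0 | 30.0 | 30.2% vs 7.7% |
| 2% | 29.9 | 29.6% vs 7.6% |
| 5% | 29.7 | 28.7% vs 7.4% |
| 10% | 29.4 | 27.2% vs 7.0% |
| 20% | 28.7 | 24.1% vs 6.2% |

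The standard error of a 40 versus 40 comparison under this model is about 7.4, so the loss at q = 5% is 0.3/7.4, or about 0.04 standard errors. These are observed-case figures. With one earlier visit added at an assumed correlation of 0.6 to 0.9, the difference was about 29.6 to 29.9 at q = 10%, so a repeated-measures model recovers part of the loss.

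**The case against.** The strongest objection is that the blanks may never arise. The scale has an explicit entry for a clear region: each severity item has 0 for none, and area has 0. A rater who follows the form enters four zeros. The documents do not describe the eCRF's entry rules and report no blank items. SAP 6.2 provides for discrepant data to be identified and queried before lock, and zero area beside blank severities is an obvious query. All of this stands, and it makes the point conditional and minor. It does not make the rule correct for a blank that survives cleaning.

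A reader might go further than the documents allow in three ways:
- *That cleared patients' scores will be lost and the active arms penalised.* No document shows this. The same blank could occur in any arm in a patient whose palms or soles were never affected, so a link with response is conjecture.
- *That any zero item saves the score.* On the severity side, all three items must be 0.
- *That every lost score becomes a failure.* Non-response imputation applies only to the binary endpoints and has the bracketing exception. The primary endpoint goes to the MMRM, where the visit is dropped and earlier visits carry part of the information. SAP 6.6.2 also names best-response imputation as a further scheme for the secondary binary endpoints.

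**Conclusion.** The point holds as a small defect in a derivation rule. SAP 9.1.1 sets PPP ASI to missing in two cases where the recorded items fix it exactly. If such a blank survives query, a known Week 16 value leaves the primary analysis. For ASI50 and ASI75 it normally counts as a failure at the Week 16 analysis.

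The size rests entirely on an unknown blank rate. It is nil if all 16 entries are mandatory. At 2% to 5% of ASI75 responders, the observed-case mean difference falls by 0.1 to 0.3 points out of 30, and by less under the MMRM. The binary endpoints are more exposed because the arms are small. The 10% and 20% rows show only how the effect scales; they are not expectations, and the documents do not support reading them as a likely bias. Severity is minor.

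**What to change.** Add to SAP 9.1.1, before the Week 16 lock: *A region with A = 0, or with E = P = D = 0, contributes 0 to PPP ASI even if its other items are blank. PPP ASI is missing only if a blank item could change its value.* Apply the same rule to the palms and soles scores.

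Two limits apply. Do not set blank severities to 0 in the by-component means: the product no longer determines the answer there, so that would be item imputation. And query any region recorded with A = 0 and a non-zero severity, so that the new rule does not hide an inconsistency.

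If the eCRF already requires all 16 entries, a sentence in 9.1.1 saying so closes the point. The cost is one or two sentences and one condition in the derivation program, decided without reference to treatment. Settling it after unblinding would be a post hoc choice on the primary endpoint.
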